2.2 Rationale for the study design

This is a phase II, open label study to determine the efficacy and safety of treatment with ceritinib in patients with a diagnosis of solid tumors or hematological malignancies that have been pre-identified (prior to study consent) to have ALK or ROS1 positive mutations, translocations, rearrangements or amplifications and whose disease has progressed on or after standard treatment.

2.3 Rationale for dose and regimen selection

The recommended ceritinib phase II dose is 750 mg/day which corresponds to the single agent recommended phase two dose (RP2D). The selection of the starting dose follows the ICH S9 guidelines for choosing a starting a dose for a first-in-human trial conducted in patients with cancer, and is shown in [Table 6-2](#). It will be dosed on a flat scale and not adjusted by weight or body surface area.

3 Objectives and endpoints

Objectives and related endpoints are described in [Table 3-1](#) below.

Table 3-1 Objectives and related endpoints

Objective	Endpoint	Analysis
Primary: 
• To assess clinical benefit associated with ceritinib treatment based on local investigator assessment.• For patients with solid tumors the assessment criteria will be RECIST 1.1 and will include responses of CR or PR or SD. For hematologic tumors other appropriate hematological response criteria will apply and are included in the appendices.	
• Clinical benefit rate (e.g. defined as CR or PR or SD \geq 16 weeks for solid tumors). For hematologic tumors, other appropriate hematological response criteria will apply and are included in the appendices.	Refer to Section 10.4
Key secondary: 
• To assess Overall Response (OR) of Partial Response (PR) or greater based on local investigator assessment.• For patients with solid tumors the assessment criteria will be RECIST 1.1 and will include responses of CR and/or PR. For hematologic tumors other appropriate hematological response criteria will apply and are included in the appendices.	
• Overall response rate (PR or greater)	Refer to Section 10.5.1
Other secondary: 
• To assess Progression-Free Survival (PFS) based on local investigator assessment per RECIST 1.1 or other appropriate hematological response criteria• To assess Overall Survival (OS)• To assess Duration of Response (DOR) based on local investigator assessment per RECIST 1.1 or other appropriate hematological response criteria• To assess safety and tolerability	
• Time from the date of first dose to the date of first documented disease progression or relapse or death due to any cause• Time from the date of first dose to the date of death due to any cause• Time from the first documented response to the date first documented disease progression or relapse or death due to any cause• Incidence of AEs, SAEs, changes from baseline in vital signs, laboratory test results(hematology, biochemistry), ECG, and cardiac imaging will be assessed by the Common Terminology Criteria for Adverse Events (CTCAE), v4.03	Refer to Section 10.5.2 Refer to Section 10.5.2 Refer to Section 10.5.2 Refer to Section 10.5.3

4 Study design

[figure not shown]
4.1 Description of study design

This is a phase II, open label study to determine the efficacy and safety of treatment with ceritinib in patients with a diagnosis of solid tumors or hematological malignancies that have been pre-identified (prior to study consent) to have ALK or ROS1 positive mutations, translocations, rearrangements or amplifications and whose disease has progressed on or after standard treatment.

This study is intended for patients who have already had genomic profiling of their tumors in a CLIA certified laboratory and have already been pre-identified to have a tumor with an ALK or ROS1 positive mutation, translocation, rearrangement or amplification. Eligibility is based on ALK or ROS1 positive mutation, translocation, rearrangement or amplification status as assessed in the local, CLIA certified laboratory. The results of this testing must be known prior to signing the ICF and before formal screening begins. Once the patient has been identified, treating physicians who are qualified investigators may contact Novartis to consider enrollment in this study. For the purpose of this study, genomic profiling is not considered part of screening. Informed consent must be signed before any screening activities take place. Once eligibility (screening criteria met) has been confirmed by Novartis, the patient will initiate therapy with ceritinib single-agent. The patient may not receive any additional anti-cancer therapy during treatment with ceritinib.

A schematic representation of the study start-up design is shown in Figure 4-1.

Figure 4-1 Study Start-up Design

4.1.1 Treatment phase

Patients will continue to receive study treatment until disease progression (assessed by investigator per RECIST 1.1 or appropriate hematologic response criteria), unacceptable toxicity, death or discontinuation from study treatment for any other reason (e.g., withdrawal of consent, start of a new anti-neoplastic therapy or at the discretion of the investigator), otherwise known as End of Treatment. All patients who discontinue from study treatment due to disease progression must have their progression clearly documented.

Disease assessments (per RECIST 1.1 or appropriate hematological response criteria) will be performed every 8 weeks (± 4 days) after first dose of study drug (Day 1 of every odd cycle), until disease progression or end of treatment, whichever occurs first. The frequency of disease assessment may be reduced to every 12 weeks for patients who have at least four post-baseline disease assessments and are clinically stable (except MM and AML patients). Scans will be assessed locally by the investigator.

4.1.2 Follow-up phase

After discontinuation of treatment, patients, regardless of reason for treatment discontinuation, will be followed for safety for 30 days after the last dose.

Survival information will be collected every 3 months until 2 years after the last patient has enrolled in the study regardless of treatment discontinuation reason (except if consent is withdrawn). If the study primary efficacy endpoint is not met, Novartis may decide not to conduct survival follow up for the study. For details on required assessments, please refer to [Table 7-1](#).

For patients with a best response of SD or better who discontinue study treatment due to disease progression, an optional tumor sample should be obtained for genomic analysis. This tumor sample must be obtained within 28 days of stopping the study treatment and no more than 14 days after starting another treatment for their cancer (at a time most convenient for the patient); exceptions may be made after discussion with the sponsor. [REDACTED]

4.2 Definition of end of the study

End of study is defined as the time when the last patient completes survival follow-up, has expired, is lost to follow up or withdraws consent, or when the study is terminated early.

The analysis of study data will be based on all patients' data up to the time when all patients have had the opportunity to complete at least 4 cycles (or 16 weeks) of treatment or discontinued the study. This will be the cut-off point for the primary clinical study report (CSR). Additional data for patients continuing to receive study treatment past the data cutoff date for the primary CSR will be reported once all patients have discontinued treatment or been lost to follow-up. It will be reported in an addendum to the CSR, as appropriate.

At the time of CSR data cut-off, if patients are ongoing after 16 weeks on treatment and benefitting, they will continue to receive treatment in the current study until enrollment into a separate protocol.

4.3 Early study termination

The study can be terminated at any time for any reason by Novartis. Should this be necessary, the patient should be seen as soon as possible for an end of treatment (EOT) visit and the assessments for EOT should be performed as described in [Section 7](#) for a prematurely withdrawn patient. The investigator may be informed of additional procedures to be followed in order to ensure that adequate consideration is given to the protection of the patient's interests. The investigator will be responsible for informing the Institutional Review Board (IRB) and/or Ethics Committee (EC) of the early termination of the trial.

5 Population

5.1 Patient population

The study population will consist of 70-90 adult patients with a diagnosis of a solid tumor or hematological malignancy that has been pre-identified as having ALK or ROS1 positive mutations, translocations, rearrangements or amplifications. Patients must have received at least one prior treatment for their recurrent, metastatic and/or locally advanced disease and have no remaining standard therapy options anticipated to result in a durable response. Patients must have progressive and measurable disease (per RECIST 1.1 or other appropriate hematological response assessment criteria) and be in need of treatment. This is a signal seeking study, attempting to identify additional patient populations who may benefit from treatment with single agent ceritinib. Tumors currently being studied under some key Novartis-sponsored trials will be excluded. This includes ALK+ NSCLC. Patients with ROS1 rearranged NSCLC may be included. Additional tumor types may be excluded during the course of the study at the discretion of Novartis.

Patients must not have symptomatic cardiac disease, or impairment of gastrointestinal (GI) function.

Enrollment is meant to encompass solid tumors and hematologic malignancies as having ALK or ROS1 positive mutations, translocations, rearrangements or amplifications that may be inhibited by ceritinib who otherwise meet the all of the inclusion and none of the exclusion criteria. Though common for phase I studies, tissue-agnostic enrollment is unusual for phase II studies, which typically limit enrollment to one or a few well-defined tumors types. We expect that the study will enroll patients whose tumors have already been pre-identified to harbor ALK or ROS1 positive mutations, translocations, rearrangements or amplifications such as B-cell lymphoma, breast cancer, colorectal cancer, melanoma, ALCL and ovarian cancer (enrollment will not be strictly limited to those particular cancers). Patients with ROS1 rearranged NSCLC may also be included. The total number of patients to be enrolled per tumor type will be based on an adaptive design. The adaptive design will be patient-sparing and allow the early closure of non-responding arms or arms where early success can be declared.

5.2 Inclusion criteria

Patients eligible for inclusion in this study have to meet **all** of the following criteria:

1. Patient has provided a signed study Informed Consent Form prior to any screening procedure
2. Patient is ≥ 18 years of age on the day of consenting to the study
3. Patient has a confirmed diagnosis of a solid tumor (except ALK+ NSCLC) or hematological malignancy and is in need of treatment because of radiologic progression or relapse. Patients with ROS1 rearranged NSCLC may be included. Additional tumor types may be excluded during the course of the study at the discretion of Novartis.
4. Patient is in need of treatment because of progression or relapse defined as:
 - radiological progression for solid tumor and lymphoma
 - for hematologic malignancies, measurable progression or relapse by appropriate criteria (see appendices)
5. Patient must have been pre-identified as having a tumor with an ALK or ROS1 positive mutation, translocation, rearrangement or amplification. The qualifying alteration must be assessed and reported by a CLIA-certified laboratory. ALK positivity as assessed by IHC or FISH are allowed.
[REDACTED]

[REDACTED]. The sample must be submitted prior to first study dose unless agreed upon between Novartis and the investigator. See [Section 7.2.4.2.1](#).

6. Patient must have received at least one prior treatment for recurrent, metastatic and/or locally advanced disease and for whom no standard therapy options are anticipated to result in a durable remission
7. **Diffuse large B cell lymphoma only:** Patient has received or is ineligible for autologous or allogeneic stem cell transplant. This does not apply to patients with Mantle cell lymphoma or follicular lymphoma
8. Patients must have measurable disease as per appropriate guidelines:
 - a. **Solid Tumors:** by RECIST 1.1 ([Appendix A](#))
 - b. **Lymphoma:** Patient has at least one measurable nodal lesion (≥ 2 cm) according to Cheson criteria ([Cheson 2007](#)). In case where the patient has no measurable nodal lesions ≥ 2 cm in the long axis at screening, then the patient must have at least one measurable extra-nodal lesion ([Appendix B](#))
 - c. **Symptomatic Multiple Myeloma:** by International Myeloma Working Group (IMWG)
 - Serum M-component of ≥ 1 gm/dL
 - Urine M-component of ≥ 200 mg/24 h
 - Patients with plasmacytoma must have a definite increase in the size; a definite increase is defined as a 50% (and at least 1 cm) increase as measured serially by the sum of the products of the cross-diameters of the measurable lesion
 - d. **Leukemia only:** Relapsed/refractory leukemia for which no standard therapy options are anticipated to result in a durable remission:

- Acute myelogenous leukemia (AML) by World Health Organization (WHO) classification or acute lymphoblastic leukemia (ALL) relapsed or refractory to standard chemotherapy; unsuitable for standard chemotherapy or unwilling to undergo standard chemotherapy. Philadelphia chromosome (Ph) positive ALL eligible if failed prior tyrosine-kinase inhibitor therapy.
 - Age > 60 years with AML not candidates for or have refused standard chemotherapy, excluding patients with acute promyelocytic leukemia (APL) or with favorable cytogenetic abnormalities [inv16, t(8;21)]
 - For patients with Chronic Myeloid Leukemia (CML) only accelerated and blast phase CML will be allowed
9. Patient has an Eastern Cooperative Oncology Group (ECOG) performance status ≤ 1 ([Appendix M](#))
 10. Patient has a life expectancy of at least 16 weeks
 11. Patients must have adequate bone marrow as described below:
 - a. Absolute Neutrophil Count (ANC) $\geq 1.5 \times 10^9/L$ (not applicable for leukemia patients)
 - b. Platelets (PLT) $\geq 75 \times 10^9/L$ (no platelet transfusion within past 14 days) (not applicable for leukemia patients)
 - c. Hemoglobin (Hgb) $\geq 8 \text{ g/dl}$ (not applicable for leukemia patients)
 12. Patient must meet the following laboratory values at the screening visit:
 - International Normalized Ratio (INR) ≤ 1.5
 - Serum amylase $\leq 2 \times \text{ULN}$
 - Serum lipase $\leq \text{ULN}$
 - Alkaline phosphatase (ALP) $\leq 5.0 \times \text{ULN}$
 - Fasting plasma glucose $\leq 175 \text{ mg/dL} (\leq 9.8 \text{ mmol/L})$
 13. All patients must have adequate organ function defined as described below:
 - a. Potassium, calcium (corrected for serum albumin), phosphorus and magnesium within normal limits (WNL). Supplementation is allowed to meet eligibility requirements
 - b. Serum creatinine $< 1.5 \text{ mg/dl}$ and/or calculated creatinine clearance (using Cockcroft-Gault formula) $\geq 30 \text{ mL/min}$
 - c. Alanine aminotransferase (ALT) and/or aspartate aminotransferase (AST) $\leq 3.0 \times$ upper limit of normal range (ULN) or $\leq 5 \times \text{ULN}$ if liver metastases are present
 - d. Total serum bilirubin within normal range or $\leq 1.5 \times \text{ULN}$ except for patients with Gilbert's syndrome who may only be included if total bilirubin $\leq 3 \times \text{ULN}$ or direct bilirubin $\leq 1.5 \times \text{ULN}$
 14. For Leukemia patients, peripheral blast counts $< 50,000 \text{ blasts/mm}^3$

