6.3.2 Permitted study treatment adjustments for ceritinib

For patients who are unable to tolerate the protocol-specified dosing schedule, dose reductions or interruptions are permitted to manage drug-related toxicities.

- When dose reduction is necessary, the dose of ceritinib may be reduced to 600 mg, QD.
- If an additional dose reduction is required, ceritinib may be reduced to 450 mg, QD.
- If an additional dose reduction is required, ceritinib may be reduced to 300 mg, QD.
- Once the ceritinib dose is reduced it cannot be re-escalated.
- All dose reductions should be based on the worst preceding toxicity.
- Patients are allowed only 3 dose reductions (to 600 mg and 450 mg, and 300 mg) as specified in ([Table 6-2](#)).

Table 6-2 Ceritinib dose modifications

Ceritinib Dose Level	Ceritinib Dose*
Starting dose level (0)	750 mg po QD
Dose level – 1	600 mg po QD
Dose level – 2	450 mg po QD
Dose level – 3	300 mg po QD**

*Dose reduction should be based on the worst preceding toxicity
**Dose reduction below 300 mg/day is not allowed. If a dose reduction below 300 mg/day is required, the patient should be permanently discontinued from ceritinib

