Grade 4 (ANC < $0.5 \times 10^9/L$)	Omit dose until resolved to \leq Grade 2, then: If resolved in ≤ 7 days, then maintain dose level If resolved in > 7 days, then $\downarrow 1$ dose level
Febrile neutropenia (ANC < $1.0 \times 10^9/L$, with a single temperature of $\geq 38.3^\circ C$ or a sustained temperature of $\geq 38^\circ C$ for more than one hour)	Omit dose until clinically resolved and neutropenia \leq Grade 2, then $\downarrow 1$ dose level

Worst toxicity (CTCAE 4.03 Grade)*	Dose Modifications for ceritinib
Thrombocytopenia	
Grade 1 (PLT < LLN - $75 \times 10^9/L$)	Maintain dose level
Grade 2 (PLT <75 and $\geq 50 \times 10^9/L$)	
Grade 3 (PLT <50 and $\geq 25 \times 10^9/L$)	Omit dose until resolved to \leq Grade 2, then: If resolved in ≤ 7 days, then maintain dose level If resolved in >7 days, then \downarrow 1 dose level
Grade 4 (PLT < $25 \times 10^9/L$)	Omit dose until resolved to \leq Grade 2, then \downarrow 1 dose level
HEPATIC	
Alkaline phosphatase and/or Gamma-glutamyl transpeptidase (GGT)	
Isolated elevations of any grade	Maintain dose level
Total Bilirubin** (for patients with Gilbert Syndrome these dose modifications apply to changes in direct [conjugated] bilirubin only)	
Grade 1 ($>$ ULN and $\leq 1.5 \times$ ULN)	Maintain dose level with liver function test (LFTs)*** monitored as per protocol
Grade 2 (>1.5 and $\leq 3.0 \times$ ULN) with AST or ALT $\leq 3.0 \times$ ULN	Omit dose until resolved to \leq Grade 1, then: If resolved in ≤ 7 days, then maintain dose level If resolved in >7 days, then \downarrow 1 dose level
Grade 3 (>3.0 and $\leq 10.0 \times$ ULN) with AST or ALT $\leq 3.0 \times$ ULN	Omit dose until resolved to \leq Grade 1, then: If resolved in ≤ 7 days, \downarrow 1 dose level If resolved in >7 days discontinue patient from ceritinib
Grade 4 ($>10.0 \times$ ULN)	Permanently discontinue patient from ceritinib
AST or ALT	
Grade 1 ($>$ ULN and $\leq 3.0 \times$ ULN)	Maintain dose level with LFTs*** monitored per protocol
Grade 2 (>3.0 and $\leq 5.0 \times$ ULN) without total bilirubin elevation to $>2.0 \times$ ULN	Maintain dose level with LFTs*** monitored per protocol
Grade 3 (>5.0 and $\leq 20.0 \times$ ULN) without total bilirubin elevation to $>2.0 \times$ ULN	Omit dose until resolved to \leq Grade 1 (or to baseline), then \downarrow 1 dose level

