Grade 4 ($>20.0 \times$ ULN) without total bilirubin elevation to $>2.0 \times$ ULN	Omit dose until resolved to \leq Grade 1 (or to baseline), then \downarrow 1 dose level
AST or ALT and concurrent Total bilirubin	
AST or ALT $>3.0 \times$ ULN and total bilirubin $>2.0 \times$ ULN in the absence of cholestasis or hemolysis	Permanently discontinue patient from ceritinib (Refer to Section 6.3.4.2 for additional follow-up)
PANCREATIC	
Amylase and/or lipase elevations (in the absence of clinical symptoms)	
Grade 1 ($>$ ULN and $\leq 1.5 \times$ ULN)	Maintain dose level
Grade 2 (>1.5 - $2.0 \times$ ULN)	Maintain dose level
Grade ≥ 3 ($> 2.0 \times$ ULN)	Omit dose until resolved to \leq Grade 1, then \downarrow 1 dose level
Note: Withhold ceritinib for acute onset of new or progressive unexplained abdominal symptoms, such as severe pain or vomiting; perform diagnostic procedures (e.g., abdominal CT scan or ultrasound) to exclude pancreatic pathology.	
RENAL	
Serum creatinine	
Grade 1 (>1 and $\leq 1.5 \times$ baseline; $>$ ULN and $\leq 1.5 \times$ ULN)	Maintain dose level
Grade 2 (>1.5 and $\leq 3.0 \times$ baseline; >1.5 and $\leq 3.0 \times$ ULN)	Omit dose until resolved to \leq Grade 1, then: If resolved in ≤ 7 days, then maintain dose level If resolved in >7 days, then \downarrow 1 dose level
Grade 3 ($>3.0 \times$ baseline; >3.0 and $\leq 6.0 \times$ ULN)	Omit dose until resolved to \leq Grade 1, then \downarrow 1 dose level
Grade 4 ($>6.0 \times$ ULN)	Permanently discontinue patient from ceritinib

Worst toxicity (CTCAE 4.03 Grade)*	Dose Modifications for ceritinib
Grade 1 (> ULN and <1.5 x ULN)	Maintain dose level
Grade 2 (≥1.5 and ≤3.0 x ULN)	Omit dose until resolved to ≤ Grade 1, then: If resolved in ≤7 days, then maintain dose level If resolved in >7 days, then ↓ 1 dose level
Grade 3 (>3.0 and ≤6.0 x ULN)	Omit dose until resolved to ≤ Grade 1, then ↓ 1 dose level
Grade 4 (>6.0 x ULN)	Permanently discontinue patient from ceritinib
GASTROINTESTINAL	
Diarrhea****	
Grade 1	Maintain dose level but adjust anti-diarrhea treatment
Grade 2 (despite maximal anti-diarrheal medication)	Omit dose until resolved to ≤ Grade 1, then maintain dose level. If diarrhea returns as ≥ Grade 2, then omit dose until resolved to ≤ Grade 1, then ↓ 1 dose level
Grade 3 (despite maximal anti-diarrheal medication)	Omit dose until resolved to ≤ Grade 1, then ↓ 1 dose level

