6.3.4.3 Guidelines for the follow-up of laboratory renal abnormalities

In case of any occurrence of serum creatinine results of grade 2, tests must be performed weekly (or more frequently if clinically indicated) until the event resolves to \leq grade 1. Subsequent monitoring must be performed every 4 weeks.

In case of any occurrence of serum creatinine \geq grade 3, tests must be performed twice weekly (or more frequently if clinically indicated) until the event resolves to \leq grade 1. Subsequent monitoring must be performed every 4 weeks. See [Table 6-4](#).

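### Inclusion 13b admits patients whose serum creatinine is already above 1.5 x ULN, but Table 6-3 does not say how such a baseline is graded on treatment or what counts as recovery

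*Protocol*

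**What the plan says.** **Entry.** Protocol Section 5.2, item 13b, asks for serum creatinine below 1.5 mg/dL "and/or calculated creatinine clearance (using Cockcroft-Gault formula") of at least 30 mL/min. Either limb is enough. Section 6.1.1 re-applies the same criteria on Cycle 1 Day 1. A stricter renal rule, in Section 7.2.2.5.5, applies only when the screening dipstick shows protein of +1 or more.

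**Dose rules.** Table 6-3 (Section 6.3.3) carries two blocks of creatinine rows under its renal heading.
- The first gives each of Grades 1 to 3 a limit in multiples of baseline and a limit in multiples of ULN, separated by a semicolon. The Grade 2 row contains "baseline; >1.5 and", followed by the ULN range.
- The second has no heading of its own and uses ULN only: "Grade 1 (> ULN and <1.5 x ULN") and "Grade 2 (≥1.5 and ≤3.0 x ULN").

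Both withhold drug in Grade 2 until Grade 1 or better. If that takes more than 7 days, the dose drops one level. For AST/ALT, by contrast, the Grade 3 and 4 rows allow recovery to "Grade 1 (or to baseline), then" a reduction.

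**Follow-up.** Section 6.3.4.3 states: "In case of any occurrence of serum creatinine results of grade 2, tests must be performed weekly", again until Grade 1 or better, and makes no exception for an elevated baseline.

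**The concern.** The entry rule and the dose rule measure renal function on different scales. Entry can be met on clearance. Dosing is governed by serum creatinine against ULN and, in one block only, against baseline. A patient the protocol chose to admit can therefore carry an entry creatinine inside the numeric range of a withhold row.

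Two things are at stake. First, sites may grade the same unchanged creatinine differently. Second, after a true rise, the written restart condition may ask for a value the patient did not have at entry. A dose reduction cannot be reversed (Sections 6.3.1 and 6.3.2). Drug withheld for more than 21 consecutive days for treatment-related toxicity is stopped for good unless the investigator sees continued benefit (Section 6.3.3). Under SAP Section 6.1, a patient with stable disease or a confirmed response who stops before 16 weeks for a reason other than progression is non-evaluable for the primary endpoint. The Appendix Q simulations expect 10 or 5 patients per cohort, so one such patient would be 10% or 20% of a cohort.

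**Working it through.** The plan gives no figure to reproduce. The check is whether item 13b and the withhold rows can overlap.

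**Inputs.** From the protocol: clearance limit 30 mL/min; creatinine limb 1.5 mg/dL; Grade 2 from 1.5 x ULN and from 1.5 x baseline. Assumed, because laboratories are local and no ULN is stated: ULN 0.9 to 1.4 mg/dL. Age, weight and sex are illustrative.

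**Formula.** Cockcroft-Gault clearance = (140 − age) x weight / (72 x creatinine), times 0.85 for women. The highest creatinine that still gives 30 mL/min is (140 − age) x weight / 2160, with the same factor for women.

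**Step 1: eligibility.** Man, 60 years, 80 kg, creatinine 2.0 mg/dL: 80 x 80 / (72 x 2.0) = 44.4 mL/min, eligible. His ceiling is 6400 / 2160 = 2.96 mg/dL.

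**Step 2: position on the ULN scale.** 2.0 mg/dL is 2.0 x ULN at ULN 1.0 and 1.54 x at 1.3. It reaches 1.5 x ULN whenever ULN is 2.0 / 1.5 = 1.33 mg/dL or less. At 1.4 it does not (1.43 x), though his ceiling of 2.96 still does (2.12 x).

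**Step 3: breadth.** Over 242 hypothetical profiles (30 to 80 years, 50 to 100 kg, both sexes), a creatinine of at least 1.5 x ULN is compatible with clearance of at least 30 mL/min as follows:

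| Assumed ULN (mg/dL) | At least 1.5 x ULN | Above 3 x ULN |
|---|---|---|
| 0.9 | 239 (99%) | 113 (47%) |
| 1.2 | 212 (88%) | 37 (15%) |
| 1.4 | 183 (76%) | 11 (5%) |

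These are shares of invented profiles, not expected frequencies. Some profiles show no overlap: a woman of 80 years and 60 kg has a ceiling of 60 x 60 x 0.85 / 2160 = 1.42 mg/dL, or 1.18 x a ULN of 1.2. If ULN is below 1.0, the creatinine limb overlaps too (1.5 / 0.9 = 1.67).

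**Step 4: an unchanged value on treatment.** Biochemistry is repeated on Cycle 1 Day 15 (Section 7.2.2.5.2). Take the man in Step 1 with ULN 1.2. Unchanged, he is at 1.0 x baseline and 2.0 / 1.2 = 1.67 x ULN. The second block makes that Grade 2. The first does so only if the semicolon means "or", or if the worse limit governs.

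**Step 5: restart after a true rise.** If he passes 1.5 x 2.0 = 3.0 mg/dL (2.5 x ULN), he is Grade 2 on both scales. Recovery on the baseline scale is 3.0 mg/dL or less. On the ULN scale it is 1.5 x 1.2 = 1.8 mg/dL or less, below his entry value of 2.0. For ULN 1.0 to 1.3 the ULN target is 1.5 to 1.95 mg/dL, still below entry. At 1.4 it is 2.1, and the problem disappears for this patient.

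**Step 6: comparison with other limits.** Outside the leukemia exemption, entry platelets are at least 75 and the hold starts below 50 x 10⁹/L. Amylase may be up to 2 x ULN and the hold starts above that. AST/ALT may be up to 5 x ULN with liver metastases and the hold starts above that. QTcF above 470 ms is excluded and the hold starts at 501 ms. None of these entry limits reaches a hold row; creatinine does.

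**The case against.** A reader might infer that some eligible patients are on hold before their first dose. The documents do not support that. Table 6-3 is titled as guidance for ceritinib-related toxicity, and Section 6.3.2 says "dose reductions or interruptions are permitted to manage drug-related toxicities". A pre-dose value can lie in a row's range without triggering the row.

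A reader might also infer that unchanged renal function alone drives a patient to the 21-day stop. It should not: that rule needs treatment-related toxicity and has an exception for benefit. Nor does a hold by itself lose the 16-week outcome, since Section 6.3.3 keeps visits and assessments going.

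The first block does use baseline, so it would be wrong to say that creatinine grading ignores baseline. The second block may be a remnant or may have lost its label. If it is set aside, the grading of an unchanged value turns wholly on the undefined semicolon. Exclusion 12 lets the investigator keep out risky laboratory abnormalities, and Section 6.3.1 allows planned variance after discussion with the sponsor.

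All of that stands, and it narrows the point. It does not supply a recovery rule for an elevated baseline. Attribution is also a limited safeguard, because raised creatinine was reported in 39 of 255 patients (15.3%) at 750 mg in Table 1-1, none Grade 3 or 4. A site could reasonably attribute a rise to ceritinib.

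**Conclusion.** The point holds as a conflict between the entry rule and the on-treatment rule. Item 13b admits patients above 1.5 x ULN, and both creatinine blocks make recovery depend on Grade 1 with no return-to-baseline route. The two blocks also disagree with each other: exactly 1.5 x ULN is Grade 1 in the first and Grade 2 in the second, and only the first uses baseline. The consequence is confined to the treatment period. It takes the form of inconsistent grading of stable values and, after a rise attributed to ceritinib, a restart target that can lie below entry.

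The arithmetic shows that this is possible for ordinary ages and weights, given an assumed ULN of 0.9 to 1.4 mg/dL. It says nothing about how often it would occur. The documents give no distribution of baseline creatinine, so the number affected among the planned 70 to 90 patients is unknown and may be small.

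**What to change.** Reconcile item 13b of Section 5.2, both creatinine blocks of Table 6-3 and Section 6.3.4.3. The revised text should state:
- which creatinine block applies, and how its baseline and ULN limits combine;
- how a creatinine already elevated at entry is graded on treatment;
- what counts as recovery for such a patient, for both restart and monitoring.

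The threshold and the clinical rule are for the sponsor to choose. The cost is amendment wording; sample size and analysis do not change.
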